# 4.6.3 Clinical Laboratory, Blood Sample

#### 4.6.3.1 Definitions and Derivations

Blood samples for determination of clinical chemistry and haematology parameters will be taken at the times detailed in the CSP, and will be assessed in a central laboratory.

In summaries, listings and figures, lab results and normal ranges will be presented in the International System (SI) unit. Eosinophils data will be presented in both SI and conventional units (eos/HPF) in summaries.

Changes in haematology and clinical chemistry variables between baseline and each postbaseline assessment will be calculated. Please refer to Section 3.3.1.2 for baseline definition. The change from baseline is defined as the post-baseline visit value minus the baseline visit value. There will be no imputation for missing values. For values recorded with a leading greater than or less than ('>', '<') symbol, the reported numeric value will be used for analysis and the value with the symbol will be included in the listings, unless otherwise specified. For example, a value of <0.01 will be analyzed as 0.01 and listed as <0.01.

Absolute values will be compared to the relevant reference range and classified as low (below range), normal (within range or on limits) or high (above range). The central laboratory reference ranges will be used for laboratory variables. All absolute values falling outside the reference ranges will be flagged.

For the purposes of haematology and clinical chemistry, baseline and maximum or minimum value post-baseline will be calculated over the entire post-baseline period, including the post-treatment period.

For the liver function tests: Aspartate Aminotransferase (AST), Alanine Aminotransferase (ALT), Alkaline phosphatase, Gamma-GT (GGT) and total bilirubin (TBL), the multiple of the central laboratory upper limit of the normal (ULN) range will be calculated for each data point.

Multiple = Value / ULN

That is, if the ALT value was 72 IU/L (ULN 36) then the multiple would be 2.

Patients who meet any of the following criteria at any point during the study will be flagged:

- AST > 3x ULN
- ALT  $\geq 3x$  ULN
- TBL  $\geq 2xULN$

### 4.6.3.2 Presentations

All continuous laboratory parameters will be summarized by absolute value at each visit by treatment group, together with the corresponding changes from baseline. The summary statistics presented will be the minimum, 1st quartile, median, 3rd quartile, maximum, mean and SD. Mean changes from baseline over time will also be plotted by treatment group.

AstraZeneca defined extended reference ranges will be used for the identification of individual clinically important abnormalities, and a shift table will be produced for each laboratory parameter to display low, normal, high, and missing values. The shift tables will present baseline and maximum/minimum on-treatment value, as applicable for each parameter.

Shift plots showing each individual patient's laboratory value at baseline and at maximum/minimum will be produced for each continuous laboratory variable. If any laboratory variables show any unusual features (high or low values or a general shift in the data points) at other time points then shift plots of these data may be produced. A diagonal line indicating no change, and horizontal and vertical reference lines indicating the limits of the AstraZeneca defined reference ranges will also be displayed on the shift plots.

Data for patients who have treatment-emergent changes outside the predefined criteria will be presented. This data presentation will include all visits for this subset of patients.

The frequency of changes with respect to normal ranges between baseline and each post-treatment time point will be tabulated. Frequencies of clinically noteworthy values (using AstraZeneca defined reference ranges) occurring during the clinical study will also be given.

Any data outside the AstraZeneca normal and extended reference ranges will be explicitly noted on the listings that are produced.

## 4.6.4 Clinical Laboratory, Urinalysis

#### 4.6.4.1 Definitions and Derivations

Urine samples for determination of urinalysis parameters will be taken at the times detailed in the CSP, and will be assessed in a central laboratory.

Urinalysis data will be categorized as negative (0), positive (+), or strongly positive (++, ++++, or >++++) at each timepoint.

For the purposes of urinalysis shift tables, baseline and maximum or minimum value post-baseline will be calculated over the entire post-baseline period, including the post-treatment period.

#### 4.6.4.2 Presentations

For urinalysis data, a shift table will be generated to present changes from baseline to EOT. The number of patients with treatment-emergent changes will also be summarized. Here, treatment-emergent changes are defined as 1) None/Trace at baseline to +, ++, ++++, at any visit after baseline or 2) Increase of at least ++.

## 4.6.5 Other Laboratory Evaluations

Not Applicable

## 4.6.6 Vital Signs and weight

#### 4.6.6.1 Definitions and Derivations

Pre-dose vital signs and weight (pulse, systolic blood pressure, diastolic blood pressure, respiration rate, and body temperature) will be obtained in accordance with the schedule provided in the protocol. Weight will be recorded in kilograms (kg).

Changes in vital signs and weight variables between baseline and each subsequent scheduled assessment will be calculated. Please refer to Section 3.3.1.2 for baseline definition. The change from baseline is defined as the post-baseline visit value minus the baseline visit value. There will be no imputation for missing values.

Body mass index (BMI) will be calculated from the height and weight as follows:

BMI 
$$(kg/m^2)$$
 = Weight  $(kg) / (Height (m))^2$ 

#### 4.6.6.2 Presentations

Vital sign parameters will be presented for each treatment group. Summary statistics for continuous variables cover n, mean, SD, Minimum, Q1, median, Q3, and Maximum. Frequency tables cover number and percentage of patients in the respective category.

For each scheduled post-baseline visit, descriptive statistics for all vital sign parameters (systolic and diastolic blood pressure, pulse, respiration rate, oral temperature) and body weight will be presented for observed values and change from baseline.

Changes in vital signs and weight will be examined according to visit window defined in Table 3. Frequencies of clinically noteworthy values occurring during the clinical study will be presented using AstraZeneca defined reference ranges, and clinically important change criteria.

All recorded vital signs data will be listed.

## 4.6.7 Electrocardiogram

#### 4.6.7.1 Definitions and Derivations

The outcome of the overall evaluation is to be recorded as normal/abnormal in the CRF, with any abnormalities being recorded as not clinically significant or clinically significant.

#### 4.6.7.2 Presentations

The Investigator's assessment of the 12-lead ECG (normal or abnormal) will be listed for all patients, along with detailing whether any abnormalities were clinically significant or not.

The number and percentage of patients with clinically significant abnormal ECGs will be summarized by treatment group. Only ECG at baseline will be included.

## 4.6.8 Other Safety Assessments

Not Applicable.

#### 5 INTERIM ANALYSIS

Not Applicable.

#### 7 APPENDIX

## 7.1 Accounting for missing data

## 7.1.1 Accounting for missing data for change in SAGED at Week 24

The amount of missing data is minimized in this study as all patients switch to receive benralizumab after the first 24 weeks and are encouraged to complete visits until they withdraw from the study even if they discontinue treatment. In addition, in the primary analyses most sources of missing data are accounted for with the composite estimand strategy that imputes outcomes for patients who discontinue randomised treatment.

This section summarizes how we will describe the pattern of and reasons for missing data from the study. It will also describe how we plan to account for missing data, including both the primary and sensitivity analyses to assess the robustness of the treatment effect under different underlying assumptions to account for missing data.

The methodology is outlined below for the change in SAGED score primary endpoint, but similar techniques may also be used for other endpoints if appropriate.

## 7.1.1.1 Missing data description

Tabular summaries for the percentage of patients by the reason for discontinuation of randomized treatment as well as for withdrawal from the study will be presented by treatment to describe why patients discontinue from randomized treatment or withdraw from the study. The time to discontinuation of randomized treatment and withdrawal from the study will be presented using Kaplan-Meier plots (overall and split by treatment related/not treatment related reason for discontinuation, as defined in Tables 6 and 7). Dependent on these outputs some of the additional exploratory analyses described below may be produced as deemed necessary to further understand the pattern of missing data.

#### 7.1.1.2 Primary analysis under the Composite Strategy Estimand

The primary analysis for the primary endpoint of SAGED at Week 24 allows for differences in outcomes over the study treatment period up to 24 weeks. In this analysis, all the data up to Week 24 visit will be included with imputation of WOCF for patients experiencing intercurrent events. The primary analysis uses the ANCOVA method, treatment group will be included as an explanatory variable along with the baseline SAGED score, region, baseline steroids use, and location of disease as explanatory variables, and assumes that missing data is missing at random (MAR) and is a direct likelihood approach (DL).

## 7.1.1.3 Sensitivity analysis under the effectiveness estimand using the Missing at Random (MAR) assumption.

An effectiveness estimand sensitivity analysis will be explored where all the data before IPD/EOT will be used. Data after the intercurrent event until Week 24 will be treated as missing and a mixed effect model for repeated measures (MMRM) analysis will be used for the remaining data. The dependent variable in the MMRM model will be the change from baseline in the continuous outcome at Week 24 visit. Treatment group, baseline values, region, baseline steroid use, and location of disease, visit, and treatment group × visit will be the covariates. The variance-covariance matrix will be assumed to be unstructured (UN). If the procedure does not converge, then the Toeplitz, first-order autoregressive (AR(1)), compound symmetric (CS), and variance components (VC) variance-covariance matrices will be tried in that order. The estimate of the treatment effect will be based on a contrast from this MMRM model.

It is noted that if the primary analysis is statistically significant, it is not necessarily expected that all sensitivity analyses will also give statistically significant results. If the results of the sensitivity analyses provide reasonably similar estimates of the treatment effect to the primary analysis, this will be interpreted as providing assurance that neither the lost information nor the mechanisms which cause the data to be missing have an important effect on the primary analysis conclusions. Based on these outputs and the drug's mechanism of action, the plausibility of the assumptions we make about missing data in the different analyses will be considered and described in the clinical study report.

## 7.1.1.4 Imputations

Sensitivity analyses using imputation techniques will include all patients with baseline and at least one evaluable post-baseline assessment prior to the occurrence of the events. The following 4 steps will be used to build the imputation datasets and perform analyses:

- 1. 100 datasets with a monotone missing pattern will be obtained, induced by Markov Chain Monte Carlo (MCMC) method on patients prior to the occurrence of the events, or Week 24, whichever comes first.
- 2. For each of the imputed datasets obtained in step 1, the remaining missing data for patients who were not rescued by Week 24 will be imputed using the regression method for the monotone pattern with adjustment for covariates including treatment groups, region, and baseline value of the response variable.
- 3. Each of the 100 imputed datasets will be analysed using the main statistical model. These 100 datasets will be saved.
- 4. Apply Rubin's rule (Rubin et al 1986, Rubin 1987) to combine analysis results (point estimates and standard errors) from 100 imputations. Descriptive statistics

including number of patients, mean, standard error, and least squares (LS) means will be provided for each timepoint. In addition, difference in LS means and the corresponding 95% confidence intervals (CI) will be provided along with the p-values for Week 24 and all earlier time points in turn.

## 7.1.1.5 Sensitivity analyses using both MAR and MNAR assumptions

As described in Section 4.2.1.5, if the amount of missing data is high enough to warrant further exploration, sensitivity analyses for the primary and key secondary endpoints based on different missing data mechanism assumptions will be used to explore the robustness of any treatment effect including multiple imputation approaches.

To examine the sensitivity of the results of the primary analysis to departures from the underlying assumptions, additional analyses may be performed using controlled multiple imputation methods introduced in [1, 2, 3] and further developed at AstraZeneca [4, 5] which allow for different underlying assumptions to be used. This model will assume that some pre-specified subset of patients who have missing data at Week 24 have correlations with future unobserved visits similar to patients in the placebo arm. The assumptions that will be used to impute the missing data are as follows:

- (a) Missing at Random (MAR): Assumes that the trajectory for patients with missing data in each arm is similar to those observed in their own treatment arm.
- (b) Dropout Reason-based Multiple Imputation (DRMI): Assumes that the trajectory for patients in the benralizumab arms who dropped out for a treatment related reason or severe non-compliance of protocol is similar to that of the placebo patients, whereas the remaining patients who has dropped out are imputed assuming MAR.

Under the primary estimand, where treatment discontinuations are handled with a composite strategy, method (a) would be used for any missing data other than treatment/study discontinuation. In addition, to explore potentially informative drop out reasons, instead of the WOCF imputation implemented in the primary analysis, methods (a) and/or (b) may be used.

A summary of reasons for patients withdrawing from the benralizumab treatment arm and the corresponding treatment arm used to calculate the imputation under MAR and DRMI are given in Table 10.

Table 10 Summary of reasons for patients withdrawing from the benralizumab treatment arm and the corresponding treatment arm used to calculate the imputation response rate under MAR and DRMI

Reason for withdrawal	MAR	DRMI	
Adverse Event	Benralizumab	Placebo	

Development of study-specific discontinuation criteria	Benralizumab	Placebo
Death	Benralizumab	Placebo
Severe non-compliance to protocol	Benralizumab	Placebo
Eligibility criteria not fulfilled	Benralizumab	Benralizumab
Subject lost to follow up	Benralizumab	Benralizumab
Subject decision	Benralizumab	Based on review prior to study unblinding
COVID-19	Benralizumab	Benralizumab
Other	Benralizumab	Based on review prior to study unblinding

Note: Patients in the placebo arm are imputed using the mean of the non-missing values in placebo arm.

Some reasons for withdrawal are clearer to determine as treatment related (AEs, Death, Development of study-specific discontinuation criteria) or non-treatment related (patients lost to follow up, eligibility criteria not fulfilled). Other reasons are less clear such as subject decision and 'Other'; a review of each patient who withdraws from the study will therefore be carried out prior to unblinding the study. Based on this review the default assumptions for DRMI as described in (b) and Table 10 may be changed. A list of these patients and the assumptions made under DRMI will be documented prior to unblinding of the study.

Forest plots will be used to show the primary analysis results along with the missing data sensitivity and alternative estimand analysis results.

It is noted that if the primary analysis is statistically significant, it is not necessarily expected that all sensitivity analyses will also give statistically significant results. If the results of the sensitivity analyses provide reasonably similar estimates of the treatment effect to the primary analysis, this will be interpreted as providing assurance that neither the lost information nor the mechanisms which cause the data to be missing have an important effect on primary analysis conclusions. Based on these outputs and the drug's mechanism of action, the plausibility of the assumptions we make about missing data in the different analyses will be considered and described in the clinical study report.

The methodology described above to explore any potential impact of missing data for the SAGED change at Week 24 endpoint may be repeated for other endpoints if appropriate.

# 7.2 Partial dates for adverse events and prior/concomitant medications

Dates missing the day or both the day and month of the year will adhere to the following conventions in order to classify treatment-emergent AEs and to classify prior/concomitant medications:

#### Adverse Events

- The missing day of onset of an AE will be set to:
  - First day of the month that the event occurred, if the onset YYYY-MM is after the YYYY-MM of first study treatment
  - The day of the first study treatment, if the onset YYYY-MM is the same as YYYY-MM of the first study treatment
  - The date of informed consent, if the onset YYYY-MM is before the YYYY-MM of the first treatment.
- The missing day of resolution of an AE will be set to:
  - The last day of the month of the occurrence. If the patient died in the same month, then set the imputed date as the death date.
- If the onset date of an AE is missing both the day and month, the onset date will be set to:

- o January 1 of the year of onset, if the onset year is after the year of the first study treatment
- The date of the first treatment, if the onset year is the same as the year of the first study treatment
- o The date of informed consent, if the onset year is before the year of the first treatment
- If the resolution date of an AE or end date of an IP is missing both the day and month, the date will be set to:
  - o December 31 of the year of occurrence. If the patient died in the same year, then set the imputed date as the death date.

#### Prior/concomitant medication

- The missing day of start date of a therapy will be set to the first day of the month that the event occurred.
- The missing day of end date of a therapy will be set to the last day of the month of the occurrence.
- If the start date of a therapy is missing both the day and month, the onset date will be set to January 1 of the year of onset.
- If the end date of a therapy is missing both the day and month, the date will be set to December 31 of the year of occurrence.
- If the start date of a therapy is null and the end date is not a complete date then the start date will be set to the earliest of the imputed partial end date and the date of the first study visit.
- If the start date of a therapy is null and the end date is a complete date
  - o and the end date is after the date of the first study visit then the start date will be set to the date of the first study visit.
  - o otherwise the start date will be set to the end date of the therapy.
- If the end date of a therapy is null and the start date is not a complete date then the end date will be set to the study end date.
- If the end date of a therapy is null and the start date is a complete date
  - o and the start date is prior to the study end date then the end date will be set to the study end date.

otherwise, the end date will be set to the start date of the therapy.

#### 8 ADDENDUM

Protocol Version 5 (Amendment 4) was issued on March 28, 2023, after the decision to close recruitment to the study early. The amendment rationale was to fulfil a commitment to participants, from when they enrolled in the trial, of open-label access to benrazilumab following double-blind treatment.

Patients that completed Part A prior to approval of amendment 4 could choose to continue to Part C, an extended open-label benralizumab treatment period. Patients in Part A and Part C, after protocol amendment approval in their respective country, will be given the option at their next clinic visit of withdrawing from the study or moving on to Part D and receiving 6 months of open-label benralizumab Q4W dosing. Patients will not complete their current treatment period. Patients who have discontinued IP during Part A are not eligible to enter Part C or D.

Enrollment was terminated after enrollment of 34 participants, of which 12 were randomized. The figure below illustrates the current study design described above.

Figure 4 Study Design Flow Chart

Q4W: every fourth week; R: reference visit number of weeks (ie, visit prior to approval of Amendment 4); EoT: end of treatment; FU: follow-up.

Given the original sample size of the study will no longer be recruited and the study will be terminated, the analysis plan for the study was updated. The amended analysis plan will now consist of descriptive summaries of safety data and select patient listings of baseline characteristics, safety data, and key efficacy data for the double-blind placebo-controlled period (part A) and the open-label period (Parts C and D). Details on the descriptive summaries can be found below in Table 11.

Principles outlined in the main SAP document related to these descriptive summaries below will apply i.e. definition of periods for safety summaries. Other analyses described in the main SAP will no longer be implemented given the small final sample size limiting the ability to assess the original study objectives.

Table 11 List of summaries for the final analyses

Summaries	Period Period	Population	Format
Subject disposition	DB + OLE	All patients analysis set	Table
Duration of exposure	DB	Safety analysis set	Table
Duration of exposure	OLE	Open-label benralizumab analysis set	Table
Adverse events in any category	DB	Safety analysis set	Table
Adverse events in any category	OLE	Open-label benralizumab analysis set	Table
Serious adverse events – key subject information	DB	Safety analysis set	Table
Adverse events causing discontinuation of study treatment – key subject information	DB + OLE	Safety analysis set	Table
Haematology and clinical chemistry, baseline to minimum/maximum value post-baseline, on-treatment	DB	Safety analysis set	Table
Haematology and clinical chemistry, post-baseline values outside central laboratory reference ranges – key subject information	DB	Safety analysis set	Table
Subjects discontinued from the study	DB + OLE	All patients analysis set	Listing
Subjects completing the study	DB + OLE	All randomized subjects	Listing
Demographic and baseline characteristics		All randomized subjects	Listing

Additional demography		All randomized subjects	Listing
EG/EGE Disease History	DB	Full analysis set	Listing
Respiratory Disease History	DB	Full analysis set	Listing
Concomitant medication during study treatment	DB + OLE	Full analysis set	Listing
Peak eosinophil count (eos/hpf)	DB + OLE	Full analysis set	Listing
PGI-S and PGI-C	DB + OLE	Full analysis set	Listing
CGI-S and CGI-C	DB + OLE	Full analysis set	Listing
Symptom Assessment for Gastrointestinal Eosinophilic Diseases (SAGED) score	DB + OLE	Full analysis set	Listing
EG-REFS Score	DB + OLE	Full analysis set	Listing
EoD-REFS Score	DB + OLE	Full analysis set	Listing
EoE-REFS Score	DB + OLE	Full analysis set	Listing
Adverse events	DB + OLE	Safety analysis set	Listing
Laboratory data – Haematology	DB + OLE	Safety analysis set	Listing
Laboratory data – Chemistry	DB + OLE	Safety analysis set	Listing
Laboratory data – Urinalysis	DB + OLE	Safety analysis set	Listing
Vital signs	DB + OLE	Safety analysis set	Listing
SAGED score change from baseline in mean value by time point, WOCF, line plot	DB	Full analysis subset	Figure

AstraZeneca 2-Oct-2023

SAGED score components mean	DB	Full analysis subset	Figure
value at Week 24, WOCF, line			
plot			

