		•	Change from baseline in proportion of vomiting- free days, and change from baseline in frequency of vomiting episodes at Week 24
		•	Change from baseline in proportion of diarrhea- free days, and change from baseline in frequency of diarrhea episodes at Week 24
		•	Change from baseline in proportion of days both diarrhea and constipation free at Week 24
		•	Time to clinically meaningful improvement in SAGED score
		•	Change from baseline in PROMIS Fatigue 7a score and PAGI-SYM score at Week 24
•	Part A: To compare the effect of benralizumab 30mg Q4W with placebo on rescue corticosteroid use	•	Key ^b : Proportion of patients with no rescue corticosteroid use up to Week 24
•	Part A: To compare the effect of benralizumab 30 mg Q4W with placebo on health-related	•	Change from baseline in SF-36v2 PCS and MCS at Week 24
	quality of life in patients with EG/EGE	•	Change from baseline in PAGI-QoL at Week 24
•	To assess the pharmacokinetics and immunogenicity of benralizumab in patients with EG/EGE	•	Serum benralizumab concentration over time Anti-drug antibodies over time
Saf	ety	 	
•	To assess the safety of benralizumab in patients with eosinophilic gastritis and/or gastroenteritis	•	Adverse Events, vital signs, physical exam, and laboratory parameters

Table 6 Objectives and Endpoints

Objectives	Estimand description/Endpoint
Exploratory	
Part A: To describe the effect of benralizumab on clinical features of EG/EGE and disease activity	Change from baseline in vomiting severity at Week 24
	Change from baseline in diarrhea severity at Week 24
	Change from baseline in endoscopic measures of inflammation and remodeling, EG-REFS, by central reader at Week 24
	Change from baseline in PAGI-SYM, DSQ, PGIS, PGI-C, CGI-S, and CGI-C
Part D: To collect more information on the safety and clinical response of benralizumab in EG/EGE.	Adverse Events, vital signs, physical exam, and laboratory parameters
	Change from baseline in CGI-S

Only restricted medications given that are considered to have a potentially meaningful impact on EG/EGE outcomes will be considered intercurrent events.

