9.4.3.1 Adverse Events

Adverse events will be coded using the most recent version of the Medical Dictionary for Regulatory Activities that will have been released for execution at AstraZeneca/designee.

Adverse events will be presented for each treatment group by system organ class and/or preferred term, including the number and percentage of participants reporting at least 1 event, number of events and exposure-adjusted rates, where appropriate.

An overview of AEs will be presented for each treatment group, including the number and percentage of participants with any AE, AEs with outcome of death, serious AEs, and AEs leading to discontinuation of investigational product.

AE listings for the safety analysis set will cover details for each individual AE, including information on the relationship to investigational product as assessed by the investigator, maximum intensity, seriousness, death and events leading to discontinuation of investigational product, as well as other action taken related to investigational product.

Key participant information will be presented for participants with AEs with outcome of death, serious AEs, and AEs leading to discontinuation of investigational product.

Full details of AE analyses will be provided in the SAP.

Treatment Emergence

The following events are considered treatment emergent:

- AEs with an onset date on or after the first dose of investigational product
- Worsening of pre-existing events on or after first dose of investigational product

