9.4.3.2 Clinical Safety Laboratory Assessments

Laboratory data for hematology and clinical chemistry will be Listed. The frequency of changes with respect to normal ranges between baseline and each post-treatment time point will be tabulated. Frequencies of clinically noteworthy values (defined in the SAP) occurring during the clinical study will also be given. Shifts from normal to abnormal between baseline and each post-baseline time point will be evaluated.

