9.4.3.3 Vital Signs and Weight

Vital sign parameters will be listed for all patients during the study.

Shifts from normal to abnormal between baseline and follow-up will be evaluated via a listing for the physical examination data.

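### SAP Table 11 limits the SAE key-information table and both laboratory tables to the double-blind period and has no physical-examination output, in conflict with Protocol 9.4

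*SAP*

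**What the plan says.** **SAP Section 8 (Addendum), Table 11.** Three tables on the safety analysis set have DB as their only period:

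- "Serious adverse events – key subject information"
- "Haematology and clinical chemistry, baseline to minimum/maximum value post-baseline, on-treatment"
- "Haematology and clinical chemistry, post-baseline values outside central laboratory reference ranges – key subject information"

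The next key-information row, on AEs that led to stopping treatment, is DB + OLE. Exposure and the AE overview each have a second, OLE table on the open-label benralizumab analysis set. AEs, haematology, chemistry, urinalysis and vital signs have DB + OLE listings. There is no physical-examination row for any period. The text before the table drops every other main-SAP analysis.

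**Protocol, as amended.** Section 9.4.1 plans descriptive safety summaries for Part A and for Parts C and D, and 9.4.3 has Parts C and D reported separately from Part A. Without a period limit, the subsections then state:

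- 9.4.3.1: "Key participant information will be presented for participants with AEs with outcome of death, serious AEs, and AEs leading to discontinuation of investigational product"
- 9.4.3.2: tabulated laboratory changes at each post-treatment time point, and "Frequencies of clinically noteworthy values (defined in the SAP) occurring during the clinical study will also be given"
- 9.4.3.3: "Shifts from normal to abnormal between baseline and follow-up will be evaluated via a listing for the physical examination data"

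**The concern.** Amendment 4 added one objective (Protocol Section 3, Table 6, listed as exploratory): "Part D: To collect more information on the safety and clinical response of benralizumab in EG/EGE". Its endpoints include physical examination and laboratory parameters. Patients first randomised to placebo receive benralizumab only in the open-label parts, and Part D runs without the IDMC. The end-of-study outputs are therefore where open-label safety will be examined. If the key-information and laboratory tables stop at the end of the DB period, that part of the record is left to line listings, although the current protocol promises more.

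**Working it through.** **1. Promise against output.**

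| Item | Protocol | Table 11, DB | Table 11, OLE |
|---|---|---|---|
| SAE key information | 9.4.3.1, no period limit | table | none |
| Discontinuation-AE key information | 9.4.3.1, no period limit | table | table |
| Laboratory shift to minimum/maximum | 9.4.3.2, each post-treatment time point | table | none (listing only) |
| Laboratory out-of-range values | 9.4.3.2, noteworthy values over the study | table | none (listing only) |
| Physical examination | 9.4.3.3, listing | none | none |
| AE overview | 9.4.3.1 | table | table |

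Three tables lack an open-label counterpart, and one promised listing is absent throughout. Table 11 has no key-information row for deaths. An open-label death would reach a key-information table only if it were also recorded as a discontinuation AE.

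**2. Can other text fill the gap?** No. The addendum keeps main-SAP principles for the outputs it lists and implements nothing else. SAP Section 2 still records no change from the protocol's analyses, so the shortfall is not declared there.

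**3. What stays visible.** Under SAP 4.6.2.2 the AE overview counts SAEs, deaths and discontinuation AEs, so the OLE overview would count open-label SAEs. Protocol 9.4.3.1 puts seriousness, intensity, causality and action taken into the AE listing. SAP 4.6.3.2 marks out-of-range laboratory values on listings.

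**4. Exposure, as a range.** Dosing every 4 weeks for 24 weeks gives 24/4 = 6 doses, which reproduces the 6 Part D doses in Protocol 2.2.1. Assume that 6 of the 12 randomised patients received benralizumab and all took 6 DB doses: 6 × 6 = 36. If k patients complete Part D and there is no Part C dosing, the open-label share of benralizumab doses is 6k/(6k + 36):

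- k = 3: 18/54 = 33%
- k = 6: 36/72 = 50%
- k = 7: 42/78 = 54%
- k = 12: 72/108 = 67%

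With an unequal split, k = 12 gives 72/(72 + 48) = 60% if 8 were on benralizumab and 72/(72 + 24) = 75% if 4 were. If 6 patients also had 6 Part C doses each (36 doses), k = 4 gives 60/96 = 63% and k = 12 gives 108/144 = 75%. Shortened Part A dosing raises the share; early stopping in Part D lowers it.

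**5. Laboratory data are a different measure.** Post-baseline haematology/chemistry is scheduled at V4, V6 and V8 in Part A, at V12 and V15 in Part C, and at V26 and follow-up in Part D, plus any discontinuation visit (Protocol Tables 1 to 3). The Part D follow-up may be a telephone contact. Dose share therefore overstates the share of laboratory results affected.

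**6. Period definition.** SAP 3.3.1.1 starts OLE at the first open-label dose at Week 24 for Part C participants and places all data of patients who do not enter OLE in DB. Read literally, a patient moving straight from Part A to Part D stays in DB, although the addendum calls Parts C and D the open-label period. Changing Table 11 periods without settling this would misplace those patients.

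**The case against.** The best defence is that little information is lost. With 12 patients and a synoptic report, a key-information table largely repeats a listing line. Section 9.4.3.1 says SAE information will be presented without requiring a table, and it leaves detail to the SAP. Open-label laboratory sampling is sparse. Clinically significant new examination findings are reported as AEs unless due to the disease (Protocol 8.2.1 and 8.3.5), so they reach the AE listing. The examination listing is also missing for Part A, so that gap is not specific to the open-label parts.

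Most of this stands, and it limits the consequence. It does not remove the conflict. Section 9.4.3.2 asks for laboratory tabulations, which a listing does not provide, and 9.4.3.3 names a listing that does not exist. Small numbers cannot explain why one key-information row covers both periods and its neighbour only one, since the same 12 patients supply both.

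A reader might infer that open-label SAEs and laboratory abnormalities go unreported, or that all active-drug exposure of former-placebo patients is left out. The documents do not support either: the OLE exposure table, the OLE AE overview and the DB + OLE listings all include them.

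**Conclusion.** The conflict between protocol and SAP is real. Open-label SAE key information, open-label laboratory shift and out-of-range tables (including those of former-placebo patients on active drug), and physical findings not reported as AEs in any period would not be presented. The underlying AE and laboratory data would still be counted or listed, so this is a gap in presentation, not a loss of data.

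A reader might also infer that the DB period holds the least benralizumab exposure. That is not established. Under the assumptions above, Part D alone ranges from 33% of doses with 3 completers to 67% with 12, and it exceeds DB only from 7 completers if there is no Part C dosing. Part D entry is optional, and the numbers entering Parts C and D are not in the documents.

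**What to change.** 1. In SAP 3.3.1.1, start OLE at the first open-label dose in Part C or Part D, so that patients moving from Part A to Part D are not left in DB. Check that the open-label analysis set in SAP Table 2, which is worded around Week 24, includes them too.
2. In Table 11, change the SAE key-information row to DB + OLE. Add OLE rows for the two laboratory tables on the open-label benralizumab analysis set.
3. For the OLE laboratory shift, use the last value before the first benralizumab dose as baseline, and state this in the table. That is the value before first investigational product for patients randomised to benralizumab, and the last value before open-label dosing for former-placebo patients. The re-set baseline in SAP 3.3.1.2 should not simply be reused: it refers only to the start of Part C, V20 has no laboratory draw, and for patients already on benralizumab it would be an on-drug value.
4. Add the physical-examination listing, DB + OLE.

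If the sponsor prefers the shorter set, the departure and its reason belong in the CSR, as Protocol 9.4 requires.

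The cost is one definition, a few Table 11 rows and a rerun on at most 12 patients. No new data are needed. The downside is a few extra short tables, the laboratory ones resting on sparse open-label data.
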